### 3.1.7 Safety Protocol Stopping Rules

The study may be halted if any of the following safety conditions are met:

1. If one or more deaths occur, we will immediately stop accrual and promptly discuss this with the NCI IRB and the FDA.
2. If two or more patients develop a Grade 3 or greater toxicity not attributable to the aldesleukin (or circumstances unrelated to the study) that does not resolve to Grade 2 within 24 hours.
3. If two patients develop Grade 3 or greater Immune Related Adverse Event (IRAE) related to aldesleukin that cannot be resolved to less than or equal to a Grade 2 within 10 days.
4. If 2 DLTs occur on dose level 1.

### **3.2 DRUG ADMINISTRATION**

Inpatient treatment will be according to the following schedule. Cell infusions may be slowed or delayed as medically indicated. Administration of diuretics, hydration, and electrolyte monitoring and replacement will be performed as clinically indicated.

#### Day 0

##### E6 TCR cells

The E6 TCR cells will be delivered to the patient care unit by an authorized staff member. Prior to infusion, the cell product identity label is double-checked by two authorized staff (MD or RN) and an identification of the product and documentation of administration are entered in the patient's chart (as is done for blood banking protocols). E6 TCR T cells will be administered intravenously over 20 to 30 minutes via non-filtered tubing, gently agitating the bag during infusion to prevent cell clumping. A peripheral IV may be used if access is adequate (in general, two 18 gauge or larger IVs should be established). A PICC line or other central line may be used if peripheral access is not adequate.

##### Prophylactic antibiotics

Prophylactic antibiotics will be administered starting the morning of cell infusion and continue until 24 hours after the last dose of aldesleukin per PI discretion. Oxacillin, clindamycin, or other antibiotic with equivalent gram positive coverage may be chosen based on patient's history of allergies and physician discretion.

#### Day 1

Beginning in the morning of day 1, Aldesleukin will be given 720,000 IU/kg IV q12 hours for up to 2 doses. Infusion will take place over 15 minutes. The second dose of aldesleukin will be given at the treating physician's discretion and will not be given if a grade 3 or higher AE occurs following the first dose.

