### 3.1.4 Treatment Phase

E6 TCR T cells will be infused while the patient is admitted to the hospital on treatment day 0. A central line catheter may be placed for cell infusion. The day after cell infusion, patients will receive aldesleukin 720,000 IU/kg IV q 12 hours x up to 2 doses. The second dose of aldesleukin will not be given if a patient develops any of the following: 1) hypotension or oliguria that require fluid boluses, 2) mental status changes, 3) hypoxia that requires supplemental oxygen, 4) diarrhea or nausea that are not controlled with symptomatic therapy. The second dose of aldesleukin may also be held for any safety concern at the discretion of the treating physician, and will not be given if a grade 3 or higher AE occurs following the first dose.

The patient will remain an inpatient for aldesleukin administration. Patients also will be observed overnight as inpatients following aldesleukin administration, and will not be discharged until cleared by the treating physician. Patients will receive one course of treatment.

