### 3.1.5 Dose Limiting Toxicities (DLTs)

All treatment related Grade 3 and greater AEs occurring within 30 days of the cell infusion will be considered DLTs with the exception of the following expected transient effects of aldesleukin.

- Grade 3 fever or chills responsive to symptomatic treatment that resolve to  $\leq$  grade 2 in 48 hours.
- Grade 3 hypotension or oliguria responsive to  $\leq$  1.5L of IV fluid boluses in 24 hours that resolves to  $\leq$  grade 2 in 48 hours.
- Grade 3 dyspnea/hypoxia that improves to  $\leq$  grade 2 or less with supplemental oxygen and resolves to  $\leq$  grade 2 without supplemental oxygen in 48 hours.
- Grade 3 creatinine or electrolyte abnormalities that resolve to  $\leq$  grade 2 in 48 hours.
- Grade 3 or higher white blood cell count decreased and/or lymphocyte count decreased that resolves to  $\leq$  grade 2 in 72 hours.

Further outline of expected AEs with aldesleukin and their management is included in [Appendix B](#) and [Appendix C](#).

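### The dosing schedule in section 3.2 carries only one of the five bars on a second aldesleukin dose set in section 3.1.4, and leaves the rest to discretion

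*Combined protocol and SAP*

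**What the plan says.** Section 3.1.4 (Treatment Phase) gives the fuller rule. Dose 2 "will not be given if a patient develops any of the following: 1) hypotension or oliguria that require fluid boluses", and the list continues: "2) mental status changes, 3) hypoxia that requires supplemental oxygen, 4) diarrhea or nausea that are not controlled with symptomatic therapy". No grade is attached to any of these four items. The section then adds a power to withhold, "The second dose of aldesleukin may also be held for any safety concern at the discretion of the treating physician", and closes with a fifth mandatory bar: any adverse event of grade 3 or higher after the first dose.

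Section 3.2 (Drug Administration) opens by presenting itself as the schedule that inpatient treatment follows. Under Day 1 it says: "The second dose of aldesleukin will be given at the treating physician's discretion". The same sentence goes on to repeat the grade 3 bar. The four numbered events do not appear, and there is no reference to 3.1.4.

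Both sections give the same dose, the same 12-hour interval and the same limit of two doses.

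**The concern.** The protocol states one safety decision twice, and the two statements differ in two respects.

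- **The list of bars.** Section 3.2 is not silent on when to withhold dose 2. It names one mandatory bar and leaves the rest to judgement, so a reader can reasonably take that list as complete.
- **The direction of discretion.** In 3.1.4 discretion only adds reasons to withhold. In 3.2 it is attached to giving the dose.

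Section 3.2 is a natural source for inpatient orders. A patient with a named event below grade 3 after dose 1 must not receive dose 2 under 3.1.4, but could receive it from a team working from 3.2 only. The patients have a premalignant condition, and sections 1.2.5 and 1.2.6 offer limited aldesleukin exposure as part of the safety margin. The four triggers belong to that limitation. Giving the dose against 3.1.4 would also be a protocol deviation, and section 7.2.1 requires every deviation to be reported within 7 days.

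**Working it through.** The plan gives no figure to reproduce here. The check is a comparison of the two texts and a count.

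**Step 1: count the bars.** Section 3.1.4 has 4 numbered events + 1 grade rule = 5 mandatory bars. Section 3.2, Day 1, has 1, the grade rule. Carried over: 1 of 5. Omitted: 5 − 1 = 4. If the paired items (hypotension and oliguria; diarrhea and nausea) are counted separately, 3.1.4 has 6 + 1 = 7 bars, of which 1 is carried over and 6 are omitted. The conclusion is the same either way.

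**Step 2: apply each section to the same patient after dose 1.**

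| Situation after dose 1 | Section 3.1.4 | Section 3.2, Day 1, read alone |
|---|---|---|
| Numbered event, below grade 3 | Dose 2 barred | Left to discretion |
| Numbered event, grade 3 or higher | Dose 2 barred | Dose 2 barred |
| Other adverse event, grade 3 or higher | Dose 2 barred | Dose 2 barred |
| Other safety concern, below grade 3 | May be withheld | Left to discretion |

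Only the first row produces a different mandatory outcome. The clearest example is "2) mental status changes": a change below grade 3 prohibits dose 2 in 3.1.4 and is a matter of judgement in 3.2.

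**Step 3: see whether another section supplies the missing bars.**

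- Section 3.6.1 stops aldesleukin only after grade 3 or 4 toxicity caused by the cell infusion.
- Section 11.1.5 covers the weight basis, infusion time and inpatient setting.
- Appendix C covers supportive treatment and whether an event counts as a dose-limiting toxicity (DLT), not whether dose 2 may be given.

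None of them restores the four events.

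**Step 4: bound the size.** For an affected patient, total aldesleukin is 2 × 720,000 = 1,440,000 IU/kg instead of 720,000 IU/kg. Not every numbered event falls in the gap. The DLT exceptions in section 3.1.5 include "Grade 3 hypotension or oliguria responsive to" a limited volume of bolus fluid, and also grade 3 dyspnea or hypoxia treated with oxygen. Some trigger events are therefore grade 3, where both sections bar the dose.

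The frequency of trigger events below grade 3 cannot be derived. Appendix B reports hypotension in 71%, diarrhea in 67%, oliguria in 63%, dyspnea in 43% and confusion in 34% of 525 patients given aldesleukin. These figures are not split by grade and do not describe one dose. They show that such events are expected, not how often the gap would arise.

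**The case against.** The strongest reply is that nothing conflicts. Section 3.1.4 is the treatment section and states all five bars in mandatory terms. Section 3.2 does not say that dose 2 may be given after a numbered event. Anyone who obeys both sections follows the stricter one, and no precedence clause is needed for that. On this view the harm requires a reader who ignores 3.1.4, and giving the dose would be a reportable deviation whatever 3.2 leaves out. The contrast in discretion is also softer than it first looks: both sections allow up to two doses, so discretion over giving dose 2 includes discretion to withhold it. The grade 3 bar, the two-dose cap, physician judgement and inpatient care hold on either reading. Finally, 1,440,000 IU/kg is the planned maximum, not an overdose.

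Most of this stands, and it limits the point. The sections are not strictly contradictory, and the remaining safeguards are real. Two things survive. First, the section written as the inpatient schedule gives a partial list that reads as complete, with no pointer to the full one. Second, deviation reporting comes after the dose has been given; it does not replace an instruction that would prevent it. The planned maximum is also not the right comparator for a patient who has already met a bar, because for that patient the protocol allows one dose only.

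**Conclusion.** The concern holds. Section 3.2, Day 1, restates the second-dose rule incompletely: 1 of 5 mandatory bars is present and 4 are missing. Followed alone, it leaves dose 2 to discretion after a named event below grade 3 for which 3.1.4 prohibits it.

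This is a gap in a safety instruction and an inconsistency between sections; the rule in 3.1.4 is itself complete. The point rests on two readings of the text: that the four events carry no grade threshold, which 3.1.4 shows, and that some of them can occur below grade 3. The protocol uses CTCAE version 4.0 but does not reproduce its grade definitions, so the events in the gap cannot be listed from the documents, and their frequency is unknown. The two-dose cap is unaffected, and no effect on DLT counts, escalation decisions or sample size is claimed. The correction should be made.

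**What to change.** Replace the last sentence of section 3.2, Day 1, with wording such as:

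*Dose 2 of aldesleukin must be withheld if any bar in section 3.1.4 has been met, that is, any of the four numbered events whatever its grade, or an adverse event of grade 3 or higher after dose 1. The treating physician may additionally withhold it on other safety grounds.*

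This brings all five bars into the dosing schedule by reference and makes discretion a power to withhold only, as in 3.1.4. Adding the four events without rewording the discretion clause would leave part of the ambiguity in place.

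The cost is one sentence. Design, sample size and procedures do not change.

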3.3 STUDY CALENDAR

Procedure	Screening/ Baseline 	Day 0	Day 1	Day 2	Day 3	Daily until d/c	Follow-up Period			
							1 wk (Days 5-8)	2 wk (Days 10-14)	Monthly f/u  (Month 1 is also End of Treatment Visit)	Annual Followup
History, physical exam, and review of systems 	X	X 	X 	X 	X 	X 	X	X	X	
Vital signs	X	X	X	X	X	X	X	X	X	
Concomitant medications	X	X	X	X	X	X	X	X	X	
ECOG performance status	X						X	X	X	
Chest x-ray	X									
EKG/Cardiac stress test (as per guidelines in Section 2.2)	X									
Screening labs: HIV, HBV serology, HCV serology, thyroid panel, PT/PTT, Beta-HCG pregnancy test, HLA-A typing for HLA-A*02:01 allele positivity	X									
HPV-16 verification and pathology review for confirmation of diagnosis 	X									
Acute care panel, hepatic panel, mineral panel, LD, total protein, CK, uric acid, CBC with differential and TBNK	X						X	X	X	

Procedure	Screening/ Baseline 	Day 0	Day 1	Day 2	Day 3	Daily until d/c	Follow-up Period			
							1 wk (Days 5-8)	2 wk (Days 10-14)	Monthly f/u  (Month 1 is also End of Treatment Visit)	Annual Followup
HSIL measurements, vulvar biopsy, and photographs 	X						X		X	
Leukapheresis	X						X			
Replication Competent Retrovirus (RCR) testing 	X								X 	
Research samples: peripheral blood lymphocytes, plasma, and serum 	X		X		X	X 	X		X	
E6 TCR T cells		X								
Aldesleukin			X							
Prophylactic antibiotics 		X 	X 	X 						
Response Evaluation									X	
HSIL and patient status update 										X
Adverse Events		X	X	X	X	X	X	X	X	

 Patients will have a full history and physical at screening, on admission to the hospital, and on follow-up visits. While inpatient, patients will have a daily review of systems and physical exam.

 Exact timeline is indicated in Section 2.2

 Vulvar HSIL must be HPV-16+ by PCR, RNA, or in situ hybridization test from a CLIA certified laboratory prior to treatment.

 Vulvar biopsies will be performed as a punch biopsy under local anesthetic in the outpatient clinic within 8 weeks prior to starting therapy, at 2-week follow-up (day 10-14), and at 1-month follow-up (day 27-34) for all patients. An additional biopsy will be obtained at the time a patient comes off-treatment (e.g. at time of progression, at time of complete response, or at 6-month visit for patients with continuing partial response). Biopsies will be performed only if technically feasible, if they do not interfere with response assessment, and if the patient provided consent. The investigators may elect not to perform biopsies at their discretion (i.e. safety concerns, patient concerns, etc.). HSIL photographs will occur at each follow up visit.

 Patients' blood samples will be obtained and undergo analysis for detection of replication competent retroviruses (RCR) by PCR prior to cell infusion and at approximately 3, 6, and 12 months post cell administration. Blood samples will be archived annually thereafter if all previous testing has been negative with a brief clinical history. The ETIB preclinical core staff will cryopreserve 2 vials of cells if possible. If less than 10 million cells are available, only 1 vial of cells will be cryopreserved.

 Research samples will be collected at screening, pre-treatment (within four weeks prior to cell infusion); posttreatment on post-therapy day 1, post-therapy day 3, thereafter any MWF while still an inpatient for one week, and thereafter weekly while still inpatient; and post-treatment at each research visit as described in section 3.5. For each time point, six 8mL CPT tubes will be drawn (5 for PBMC and 1 for plasma) and one 8mL SST tube (for sera). Processing and storage are as described in section 5.

 Prophylactic antibiotics will be administered starting the morning of cell infusion and continue until 24 hours after the last dose of aldesleukin per PI discretion. If patients are discharged prior to completing antibiotics they will be given a prescription to complete the course at home. Oxacillin, clindamycin, or other antibiotic with equivalent gram positive coverage may be chosen based on patient's history of allergies and physician discretion.

 All patients follow-up 1, 2, and 3 months after cell infusion. Patients with no response at the 3-month evaluation will come off-treatment and receive standard of care therapy. Patients with a partial or complete response at the 3-month evaluation will continue follow up at 4, 5, and 6 months for safety, response, and research evaluations. After the 6-month response assessment patients with partial response will receive standard of care therapy and patients with a complete response will continue to have follow-up every 3 months (+/- 30 days) for 2 visits, then every 6 months (+/- 30 days) for 2 visits (2 years of follow up total). Patients with disease progression at any time will come off treatment and receive standard of care therapy either at the NIH, with their primary physician, or another institution. For follow up visits, if unwilling or unable to travel to the NIH Clinical Center, patients will be contacted by telephone regarding their status, and may be asked to send labs and physical exam reports to fulfill follow up visit requirements. Adverse events associated with standard of care therapy will not be recorded or reported on this study.

As indicated in 3.5 (+/- 14 days)

As indicated in section 10.4, all subjects  $\geq$  age 18 will be offered the opportunity to complete an NIH advanced directives form. This should be done preferably at baseline but can be done at any time during the study as long as the capacity to do so is retained. The completion of the form is strongly recommended, but is not required.

As indicated in section 3.5.2, subjects will be contacted to collect information annually for five years after the date of cell infusion. This follow up can be conducted via telephone.

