#### 3.4.3 During Hospitalization:

Every 1-2 days.

- Daily review of systems and physical exam
- Other tests will be performed as clinically indicated.

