### 3.5 POST TREATMENT EVALUATION (FOLLOW-UP)

Follow-up visits will be done according to the following schedule.

- 1 week safety and research visit (days 5-8)
- 2 week safety and research visit (days 10-14)
- 1 month safety, research, and response visit (+/- 7 days)
- 2 month safety, research, and response visit (+/- 7 days)
- 3 month safety, research, and response visit (+/- 7 days)
- 4 month safety, research, and response visit (+/- 7 days)
- 5 month safety, research, and response visit (+/- 7 days)
- 6 month safety, research, and response visit (+/- 7 days)
- As clinically indicated subsequently.

Note: Patients may be seen more frequently as clinically indicated

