### 13.3 APPENDIX C: EXPECTED ALDESLEUKIN TOXICITIES AND THEIR MANAGEMENT

Toxicity	Grade	Supportive Medications	Considered DLT*
Chills	3	IV Meperidine 25-50mg IV q1hr, prn	No
Fever	3	Acetaminophen 650mg po q4hr; Indomethacin 50-75mg po q8h	No
Pruritus	3	Hydroxyzine HCl 10-20mg po q6h, prn; Diphenhydramine HCl 25-50mg po q4h prn	No
Nausea/Vomiting/Anorexia	3	Ondansetron 10mg IV q8hr prn, Granisetron 0.01 mg/kg IV qday prn, Droperidol 1mg IV a4-6h prn; Prochlorperazine 25mg PR prn or 10mg IV q6hr prn	No
Diarrhea	3	Loperamide 2mg po q3h prn; Diphenoxylate HCl 2.5mg and Atropine sulfate 25mcg po q3h prn; Codeine sulfate 30-60mg po q4h prn	If uncontrolled after 48h despite all supportive measures
Malaise	3 or 4	Bedrest	If other toxicities occur simultaneously
Hyperbilirubinemia	3 or 4	Observation	Yes
Anemia	3 or 4	Transfusion with PRBCs	Yes
Thrombocytopenia	3 or 4	Transfusion with platelets	Yes
Edema/Weight gain	3	Diuretics prn	No
Hypotension	3	Fluid resuscitation, Vasopressor support	No, unless requires more than 1.5L/24 hours of bolus IV fluids or vasopressor support
Dyspnea	3 or 4	Oxygen or ventilator support	If requires more than nasal cannula oxygen support or requires oxygen for greater than 48 hours after last dose

Toxicity	Grade	Supportive Medications	Considered DLT*
Oliguria	3 or 4	Fluid boluses	If requires more than 1.5L/24 hours of bolus IV fluids
Increased Creatinine	3 or 4	Observation	If grade 3 lasts more than 48 hours or for any grade 4.
Renal Failure	3 or 4	Dialysis/CVVH	Yes
Pleural Effusion	3	Thoracentesis	Yes
Bowel Perforation	3	Surgical intervention	Yes
Confusion	3	Observation	Yes
Somnolence	3 or 4	Intubation for airway protection	Yes
Arrhythmia	3	Correction of fluid and electrolyte imbalances; chemical conversion or electrical conversion therapy	Yes
Elevated Troponin Levels	3 or 4	Observation	Yes
Myocardial Infarction	4	Supportive care	Yes
Elevated Transaminases	3 or 4	Observation	Yes
Hyperbilirubinemia	3 or 4	Observation	Yes
Electrolyte Imbalances	3 or 4	Electrolyte replacement	If uncontrolled after 48 hours despite all supportive measures
Neutropenia	4	Observation	Yes

\*Unless the toxicity is not reversed within 24 hours of last aldesleukin, in which case all AEs are considered DLTs.

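### Scheduled tests do not ensure that laboratory-based DLT exceptions are detected and timed against their 48- and 72-hour limits

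*Combined protocol and SAP*

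**What the plan says.** Section 3.1.5 sets the default: treatment-related Grade 3 and greater events "occurring within 30 days of the cell infusion will be considered DLTs", apart from five listed transient effects of aldesleukin. Two of the five rest on chemistry or blood counts. One is "Grade 3 creatinine or electrolyte abnormalities that resolve to" grade 2 or less in 48 hours. The other is "Grade 3 or higher white blood cell count decreased and/or lymphocyte count decreased that resolves to" grade 2 or less in 72 hours.

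Appendix C repeats the creatinine limit (a DLT "If grade 3 lasts more than 48 hours or for any grade 4"), but its footnote runs on another clock: "Unless the toxicity is not reversed within 24 hours of last aldesleukin, in which case all AEs are considered DLTs".

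In the Section 3.3 calendar, the row for "Acute care panel, hepatic panel, mineral panel, LD, total protein, CK, uric acid, CBC with differential and TBNK" is marked at screening/baseline, week 1 (days 5-8), week 2 (days 10-14) and monthly. It is blank for days 0 to 3 and for the daily column up to discharge. The day 1 and day 3 draws are research tubes (footnote 6), not clinical chemistry or counts.

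Section 3.4.3 opens with a frequency of one to two days but names no test beside it, then adds a daily examination and "Other tests will be performed as clinically indicated". Section 3.2 provides for electrolyte monitoring on the same discretionary basis. Section 3.1.4 keeps patients in hospital overnight after aldesleukin and until the physician clears them. Calendar footnote 7 anticipates discharge before the antibiotic course ends, and that course runs to 24 hours after the last aldesleukin dose.

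**The concern.** Whether these laboratory events are exempt depends on when they began and when they resolved. Aldesleukin is given on day 1, so the relevant abnormalities can be expected in the days just after it, where the calendar schedules no chemistry or blood count. An asymptomatic Grade 3 value in that interval can go unseen, or can first appear at days 5-8 with no known onset.

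Safety is the primary objective, and DLT counts determine both escalation and the MTD. With three to six patients per level, a difference in how often blood is drawn, between patients or between dose levels, can change the decision without any difference in toxicity.

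Such events are plausible. Appendix B lists creatinine increase in 33% and leukopenia in 16% of aldesleukin patients. It gives no grades and is not tied to this trial's two-dose cap, so these are not predicted DLT rates.

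**Working it through.** **The plan's own figures (Section 8).** Two dose levels × 6 patients = 12 to determine the MTD; 12 + 6 = 18 in all. Both reproduce, and nothing here changes them.

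**Early timing.** Inputs: infusion is day 0; aldesleukin starts on the morning of day 1, taken as day 1.0, with a possible second dose 12 hours later at day 1.5 (Section 3.2); the first scheduled draw is on days 5 to 8 (Section 3.5). Window end = onset + 2 or + 3 days. Lag = (draw day − onset) × 24 hours.

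| Onset (day) | 48 h ends | 72 h ends | Hours to a day-5 draw | Hours to a day-8 draw |
|---|---|---|---|---|
| 1.0 | 3.0 | 4.0 | 96 | 168 |
| 1.5 | 3.5 | 4.5 | 84 | 156 |
| 2.0 | 4.0 | 5.0 | 72 | 144 |
| 2.5 | 4.5 | 5.5 | 60 | 132 |
| 3.0 | 5.0 | 6.0 | 48 | 120 |

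For onset on day 1, both windows have closed before any scheduled draw. For onset at day 2.0, the 48-hour window has closed, and only a day-5 draw meets the 72-hour limit, exactly at its edge. A draw inside the window also helps only if the onset was seen, and no scheduled test would show it.

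**Discharge.** If the second dose is at day 1.5, antibiotics end at day 2.5, and footnote 7 allows discharge before then. The earliest end of a 48-hour window that opens after aldesleukin is 1.0 + 2 = day 3.0. The gap from such a discharge to the next scheduled value is at least 5 − 2.5 = 2.5 days for a day-5 visit and 8 − 2.5 = 5.5 days for a day-8 visit.

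**Rest of the 30-day DLT period.** Week 1 to week 2: from 10 − 8 = 2 to 14 − 5 = 9 days. Week 2 to month 1, taken as day 30 ± 7 as in Section 3.5: from 23 − 14 = 9 to 37 − 10 = 27 days. These gaps nearly always exceed 2 to 3 days.

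**The two clocks.** Suppose a Grade 3 creatinine value appears at day 1.5, when the last dose is given, and resolves 36 hours later at day 3.0. Section 3.1.5 exempts it (36 < 48). The Appendix C footnote makes it a DLT, because it was not reversed by day 2.5.

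**Effect on escalation.** Under the dose level -1 rule in Section 3.1.6, with p the probability of a counted DLT per patient:

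P(cleared) = (1−p)³ + 3p(1−p)² × (1−p)³

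The documents give no rates. As an illustration, assume 10% of patients have a clear DLT and a further 10%, 20% or 30% have only an untimed Grade 3 laboratory event.

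- Untimed events treated as exempt, p = 0.1: 0.729 + 0.243 × 0.729 = 0.906.
- Counted as DLTs, p = 0.2: 0.512 + 0.384 × 0.512 = 0.709.
- Counted as DLTs, p = 0.3: 0.343 + 0.441 × 0.343 = 0.494.
- Counted as DLTs, p = 0.4: 0.216 + 0.432 × 0.216 = 0.309.

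**The case against.** A reader might infer that DLT status for these events cannot be determined at all. The documents do not support that. Patients are in hospital around aldesleukin and leave only when cleared, the adverse-event row is marked on every inpatient day, electrolyte and other tests may be ordered when indicated, and Section 6.1 follows clinically significant laboratory findings to baseline or stabilization. When those provisions are used, status can be determined. None of them, however, sets a test or retest time tied to 48 or 72 hours, and following a detected finding does nothing for one that was never detected.

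A reader might also infer that the plan has no rule for an event lacking a value inside its window. Section 3.1.5 largely answers this: DLT is the default and timely resolution is the condition for exemption, so a detected event without documented resolution does not qualify. Undetected events and those of unknown onset remain open.

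The bare frequency in Section 3.4.3 may be the remnant of an inpatient laboratory list. This cannot be confirmed. If it is, inpatient detection improves, but the interval from discharge to days 5-8 is still uncovered.

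The scope is limited. Three of the five exceptions (fever or chills, hypotension or oliguria, dyspnea or hypoxia) do not rest on chemistry or counts and are largely covered by vital signs and daily examination. The timed examples also presuppose that someone drew blood at onset; they show where the windows fall, not how often the problem will occur.

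**Conclusion.** The point holds as a gap in assured ascertainment: scheduled tests can neither detect an early laboratory abnormality nor time its resolution against the limits in Section 3.1.5, so classification rests on discretionary testing.

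The size is one patient. Moving from 1 of 6 to 2 of 6 stops the study at dose level -1. At dose level 1 it stops treatment at that level, returns accrual to level -1 if only three patients were treated there, and meets a condition in Section 3.1.7 under which the study may be halted. How often this would happen cannot be derived from the documents; the probabilities above rest on assumed rates and describe the two extreme handlings of untimed events.

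The conclusion assumes that the calendar columns are read correctly. In the copy reviewed, the leukapheresis mark sits under week 1 although the text places the procedure at week 2, so positions deserve a check. A one-column shift in the laboratory row is unlikely: it has marks in all three follow-up columns and none in the inpatient columns, whereas the vital-signs row is marked throughout.

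**What to change.** 1. Reconcile the 48- and 72-hour limits in Section 3.1.5 with the 24-hour clock in the Appendix C footnote. Do this first, because the retest times depend on it.
2. Reconcile Sections 3.1.5, 3.3 and 3.4.3: mark the chemistry and blood-count row in the inpatient columns, and name the tests to which the frequency in Section 3.4.3 applies.
3. Add a repeat value at the end of the applicable resolution window for any Grade 3 or higher laboratory value, including after discharge.
4. State explicitly, as Section 3.1.5 implies, that an event without documented resolution inside its window does not qualify for the exception.

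The cost is a change to the calendar and wording, a few extra routine blood draws, and some events classified conservatively. The planned numbers of 12 and 18 stay as they are.

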- Optional biopsies for research purposes will be obtained at baseline (within 8 weeks prior to starting treatment); at 2 week (day 10-14) safety and research visit; at 1 month (day 27 to 34) safety, response, and research visit; and at the time the patient comes off-treatment (i.e. attains a complete response, experiences progression, or reaches the 6-month time point without a complete response). Biopsies will be performed only if technically feasible, if they do not interfere with response assessment, and if the patient provides consent. The investigators may elect not to perform biopsies at their discretion (i.e. safety concerns, patient concerns, etc.). Biopsies for clinical concern will be performed as clinically indicated. Biopsies will be processed as per Section 5.1.3.
- An approximately 5 liter leukapheresis will be performed at the 2 week (day 10-14) follow up visit. If the patient is unable to undergo apheresis, approximately 96 ml of blood may be obtained. Subsequently, approximately 60 ml of blood will be obtained at each response visit (see **Study Calendar** for sampling details). Peripheral blood mononuclear cells will be cryopreserved for immunologic testing and will be banked under protocol 16-C-0061 (ETIB Tissue Procurement Protocol). PBMC from apheresis will be stored in 10 vials at 1x10^8 cells per vial with remaining cells stored at 3x10^8 cells per vial.
- Cervical testing for high-risk HPV if the screening assessment was positive for HPV-16.
- The following information will be collected annually for a total of five years after the date of cell infusion: 1) procedures or treatments for vulvar HSIL, 2) procedures or treatments for cervical, vaginal, or anal intraepithelial neoplasia, 3) occurrence of vulvar, cervical, or anal cancer.

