### **3.6 CRITERIA FOR REMOVAL FROM PROTOCOL THERAPY AND OFF STUDY CRITERIA**

Prior to removal from study, effort must be made to have all subjects complete a safety visit approximately 30 days following the last dose of study therapy. Since patients will be completing a one-month follow up visit, the end of treatment visit will be the 30 day followup visit as indicated on the Study Calendar in Section 3.3

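### The month-1 safety visit has three inconsistent windows; under each it can fall before the 30-day DLT period ends, with no further assessment guaranteed until month 2

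*Combined protocol and SAP*

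**What the plan says.** Section 3.1.5 sets the DLT period: "All treatment related Grade 3 and greater AEs occurring within 30 days of the cell infusion will be considered DLTs", apart from listed transient aldesleukin effects. Section 3.1.6 builds the 3+3 decisions and the MTD on that count.

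The visit meant to close the period is month 1. The Study Calendar (3.3) labels the monthly column "Month 1 is also End of Treatment Visit", and section 3.6 adds that "the end of treatment visit will be the 30 day followup visit as indicated on the Study Calendar".

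The timing of that visit is given in three places:

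- Section 3.5: "1 month safety, research, and response visit (+/- 7 days)".
- Study Calendar footnote 9, attached to the monthly follow-up column: "As indicated in 3.5 (+/- 14 days)".
- Section 3.5.2, in the item on optional research biopsies: "at 1 month (day 27 to 34) safety, response, and research visit". Calendar footnote 4 gives the same range.

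The scheduled visit before it is the "2 week safety and research visit (days 10-14)". The one after it is month 2.

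**The concern.** Footnote 9 misreports the section it cites, and the visit that should close the DLT period has no single date range. More importantly, none of the three ranges starts at day 30. A site can comply with the plan and hold the visit while the DLT period is still running. Nothing then obliges anyone to review adverse events or draw blood between day 30 and month 2.

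The 3+3 count treats each patient as DLT-free through day 30. With three to six patients per dose level, one unseen event can turn a count of one into zero, or of two into one. An abnormality that causes no symptoms has to be measured to be known. Grade 3 transaminase or bilirubin elevation is an example: it has no exception in section 3.1.5, and Appendix C lists it as a DLT.

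**Working it through.** **Step 1: check footnote 9 against its source.** Section 3.5 lists months 1 to 6, each with +/- 7 days. It gives +/- 14 days nowhere. The footnote's figure does not reproduce.

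**Step 2: earliest visit and days left over.** Inputs: infusion on day 0; DLT period to day 30 (3.1.5); month 1 taken as day 30, from the 30-day label in 3.6. Formulas: earliest visit = 30 − window; days of the DLT period after that visit = 30 − earliest visit.

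| Source | Visit range | Days left after earliest visit | Share of 30 days | Month 2 (taken as day 60) |
|---|---|---|---|---|
| 3.5.2 and footnote 4 (biopsy text) | 27 to 34 | 30 − 27 = 3 (days 28–30) | 10% | not given there |
| 3.5, +/- 7 | 23 to 37 | 30 − 23 = 7 (days 24–30) | 23% | 53 to 67 |
| Footnote 9, +/- 14 | 16 to 44 | 30 − 16 = 14 (days 17–30) | 47% | 46 to 74 |

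**Step 3: sensitivity to the length of a month (an assumption).** With a 28-day month the remainder is 9 days (+/- 7) or 16 days (+/- 14). With 31 days it is 6 or 13. The finding does not depend on the convention.

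**Step 4: does other text close the gap?**

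- Section 6.1 requires adverse event follow-up for at least 30 days after removal from study treatment, or until off-study if sooner. It sets no contact or test at day 30.
- Section 7.3 requires immediate reporting of serious events in the first 30 days. That covers serious events once known, not silent laboratory changes.
- Calendar footnote 8 and section 3.5.3 let remote contact stand in for a visit. Laboratory reports may then be requested but are not required.
- The biopsy range is attached to a procedure that may be declined or omitted, so it does not guarantee a late assessment. It can itself end three days short.
- Section 3.1.6 sets a minimum of 14 days between cohorts, and section 7.5.1 bases escalation on toxicity data from prior patients. Neither asks for a day-30 assessment first.

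**Step 5: direction of error.** Under section 3.1.6 a dose level passes with 0 of 3 DLTs, or with 1 of 3 followed by 0 of 3. For DLT probability p, P(pass) = (1−p)³ + 3p(1−p)²·(1−p)³, which falls as p rises, so unseen events raise it. As illustration only, assume p = 0.33: P(pass) is 43%. If 10%, 25% or 50% of DLTs went unseen, it would be 50%, 61% or 78%. The documents supply none of these inputs, so these are not estimates for this trial.

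**The case against.** The strongest reply is that the practical gap is small and partly covered. DLTs are defined by when they occur, not when they are found, so a month-2 finding with onset by day 30 still counts. Serious events must be reported, extra visits are allowed when clinically indicated, and the team reviews each patient every two weeks during active treatment (7.5.1). Aldesleukin is given from day 1, and laboratory tests are scheduled at days 5–8 and 10–14, so its expected liver effects may well appear by then. The documents give no rate of first onset after day 16 or 23. All of this stands, and it narrows the exposure to non-serious, asymptomatic laboratory events.

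Three stronger readings are tempting, and the documents do not support them.

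- A reader might infer that nothing scheduled looks at the patient at or after day 30. Month 1 may itself fall on or after day 30 under every window, and months 2 and 3 carry adverse event review and laboratory tests for all patients. What is missing is a guaranteed assessment between day 30 and month 2.
- A reader might take 14 days, or 47%, as the size of the gap. That needs footnote 9 read alone, against section 3.6, which places the safety visit about 30 days after the last dose. Day 16 does not fit that description.
- A reader might infer that the early visit is what lets a dose decision precede complete DLT data. The 14-day between-cohort minimum allows that whatever the visit window, so reconciling the windows alone would not change it.

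**Conclusion.** The inconsistency is certain: one visit, three windows, one of them wrongly attributed. The consequence is limited but bears on the primary endpoint. With month 1 at day 30, up to 3 days (biopsy range) or 7 days (section 3.5) of the DLT period can follow the last scheduled assessment before month 2, and 14 days only on footnote 9 read alone. These are permitted worst cases; a visit on or after day 30 leaves no gap.

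Any resulting error runs towards too few DLTs. Its effect on the MTD cannot be computed, because the documents give neither a DLT rate nor a distribution of onset times. The point should be corrected, but it does not show that the dose finding is invalid.

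**What to change.** 1. Give the month-1 visit one window, stated identically in 3.3 (footnotes 4 and 9), 3.5, 3.5.2 and 3.6, and correct footnote 9.
2. Align that window with the 30-day DLT period. Record a patient's DLT status as complete only on an adverse event review and the already scheduled chemistry and blood count obtained on or after day 30. A window of days 30 to 34, for example, would also meet the biopsy range.
3. Reconcile the 14-day between-cohort minimum in 3.1.6 with the 30-day DLT period. Which interval applies is for the sponsor to settle.

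**Cost.** No new visit, test or patient is needed, but item 2 is a new rule and not only a wording correction. On the example window, scheduling freedom at month 1 drops from 15 days (23 to 37) to 5 (30 to 34), which matters for patients who travel. If dose-level decisions use completed DLT status, and the 14 days run from the last infusion in a cohort, the earliest decision moves by 30 − 14 = 16 to 34 − 14 = 20 days.
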